# Selection and Withdrawal of Subjects

Lower limb transfemoral amputees will be recruited from inpatient and outpatient amputee clinics at The Rehabilitation Institute of Chicago and Northwestern Memorial Hospital. Criteria will be:

## **Inclusion criteria**

- Males or females with dysvascular transfemoral amputations
- 6 months or more post prosthetic fitting
- Homebound or limited community ambulators post amputation
- Ability to walk >50m in a 2 min walk test

#### **Exclusion criteria**

- Traumatic, cancer or genetic amputation
- Co-morbidity that completely prevents physical activity
- Significant skin lesions/ulcers on stump that prevent fitting of prosthesis
- Cognitive deficits or visual impairments that would impair their ability to give informed consent or to follow simple instructions during experiment

#### Withdrawal criteria

- 3 or more consecutive or 5 total per leg missed sessions
- Hospitalizations
- At PI's discretion for unforeseen/unplanned medical events that may alter inclusion or exclusion criteria

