# 4) Research Methods: Study Design:

The study will have a randomized, repeated measures design. Due to the high rate of attrition we will randomize a total of 40 subjects, 20 into each of the groups below.

Group I

Mech Knee+Old Foot	C-leg + New Foot	C-Leg + New Foot	Mech knee + New Foot	Mech knee + New Foot
>6 months post TF prosthetic fitting	Acclimation	Assessment	Acclimation	Assessment
Duration	3 months	3 months	3 months	3 months
Data Collection	Monthly	Monthly	Monthly	Monthly

Group II

Mech Knee+Old Foot	Mech Knee + New Foot	Mech Knee +New Foot	C-Leg+ New Foot	C-Leg+ New Foot
>6 months post TF prosthetic fitting	Acclimation	Assessment	Acclimation	Assessment
Duration	3 months	3 months	3 months	3 months
Data Collection	Monthly	Monthly	Monthly	Monthly

All measures will be administered and data collected under the supervision of a licensed physical therapist.

- I. Assess and compare mobility in TF amputees:
  - a. To quantify community ambulation including time spent out of the home, use of public transport, GPS technology will be used. Subjects will be required to wear a GPS monitor on their belts during the day. This will track their activities in their homes and in the community.
  - b. To assess functional mobility the Amputee Mobility Predictor will be used. A standardized sequence of mobility tests with the prosthesis will be administered on the first pre-acclimation session. The patient will be scored out of 39.
  - c. To quantify fall risk and functional mobility the Timed Up and Go (TUG) test will be used. TUG is the time taken for the subject to get up from chair, walk 3 meters and sits down; measured in seconds.
  - d. To objectify the amount of steps in ADLs and functional mobility the Step Activity Monitor will be used. The subject will be given a monitor that he/she will have to wear around his/her ankle. This will record the number of steps.
  - e. To determine community and social participation, the Community Participation Indicators questionnaire will be used. It is a valid, new generation of self-report outcome measure for community participation. It will take 15-30 minutes to complete and will be administered in room 1771.
- II. Assess and compare gait distance and speed:

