# **Data Collection and Analysis**

Subjects will be screened and medical history and information relevant to why and when they received an amputation will be accessed from their medical records. Subjects will be explained the study design, procedures, tests, questionnaires and physical therapy visits asked to sign an informed consent prior to participating in the study. After subjects are randomized into two groups, they will be provided with a GPS device and a step activity monitor which will track their walking/mobility patterns at home and in the community for 4 weeks. When they return, over 1-2 visits, they will be assessed for a full battery of baseline outcome measures: six minute walk test (6 mwt), Amputee Mobility Predictor (AMP), Timed Up and GO (TUG), BERG balance test,. They will also be required to fill in self-report questionnaires for falls and the PEQ. They will then be fitted with the randomized prosthesis and new foot by a certified prosthetist. There will a period of acclimation for 3 months during which patients will be provided physical therapy with either the C-leg with a new foot or a mechanical leg with a new foot. Subjects will come for an average of two times a week for physical therapy training. The pre-training visits will include 1 for informed consent and GPS, 1-2 for evaluation and an additional 1-2 for prosthetic fit. The training sessions will be a maximum of 14. There will also be 1-2 reassessment visits. This will be repeated for the other prosthesis. There will be a maximum total of up to 45 visits. Subjects will be compensated \$40 per session for evaluation and assessments, prosthetic fittings and training sessions. This is the usual amount in similar studies and other studies at the Rehabilitation Institute of Chicago. The total compensation will be determined by the number of sessions that the subject completes while enrolled in the study. There will be 2 sessions allowed for a subject to be paid, even if they arrive but are unable to complete a session due to unscheduled issues (such as illness). However, if patients miss 3 or more consecutive visits, or experience a medical illness that may/may not require hospitalization, patients may have to be withdrawn from the study. Patients will be offered the additional service of adjustments for prosthesis/refining home exercise program in phone or in person, but they will not be compensated for these patient initiated services.

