The training will focus on providing both groups 1) strength training for upper limbs, core and lower limbs, 2) functional training, e.g. sit – stand, gait training on level surfaces, community ambulation and 3) cardiovascular and endurance training. The following 3 months there will be an assessment period for that particular knee and foot combination. In the course of the assessment period, patients will come in at regular intervals for data collection for the AMP and the 6 mwt. During the last 2 weeks of the assessment, patients will be given GPS devices for tracking their mobility data. At the end of 6 months there will be a crossover where patients with the mechanical leg will receive a new C leg + new foot and patients with the C leg will receive a mechanical leg + new foot. Once again, this will be followed by baseline testing, a period of 3 months acclimation with physical therapy sessions and a 3 month period of assessment where patients will come in for data collection. In the last 2 weeks, GPS data will be collected. The data collected will be analyzed for differences in outcome measures caused by the different prosthetic devices.

During the data collection process and the training sessions, a licensed physical therapist will be present to provide supervision and monitoring of the patient's vitals, signs and symptoms. During the sessions, subjects may be photographed or videotaped performing assessments, functional tasks, or exercising, with their consent. The photos and video recordings will not include the subjects face and if used for presentations or publications, will not identify the subject. The data collection and the training sessions will be terminated if the subjects expresses that he/she is unable/does not wish to participate. Subjects will be compensated \$40 per session. Payment will be in cash or by ClinCard per session, at the end of each session. RIC is moving away from using petty cash. During this transition period the subject may be paid in cash or by ClinCard. If a ClinCard is available when you come for the the study, you will be paid by card. If a ClinCard is not available, then you will receive cash payments.

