If the subject is issued a ClinCard, which is a specially designed debit card for clinical research, the funds will be loaded as appropriate. When a visit is completed, funds will be approved and loaded onto the card. The funds will be available within 1 day after being loaded and can be used at the subject's discretion. The subject will be issued one card for the duration of your participation. If your card is lost or stolen, please call [contact] or ask a coordinator for a replacement ClinCard.

Fees are incurred if used at an ATM (fees vary by location). However, if the card is used for in-store or online purchases via credit or debit, or presented to a bank teller, there are no associated fees and no expiration date.

If subjects wish to join RIC's gym to exercise to increasing endurance and fitness, we will provide them membership (with an RIC physician signing membership form) to RIC's Fitness Center and Sports Program (a \$35 cost that the study will pay to the Fitness Center for the subject). Subjects may be required to participate in a maximum of 45 sessions, although the maximum may not be needed for all subjects. The maximum

compensation is \$1800, although the total compensation will be determined by the number of sessions that the subject completes while enrolled in the study.

The data collected will be analyzed offline. All data and medical information of potential subjects will be locked in a file cabinet in the office of the PI. All study personnel listed will have access to the data and medical information. Subjects will be assigned a code when they are enrolled in the study. All GPS data will be analyzed by a researcher who is blinded to the subjects' identity. All data will be kept on computer hard-drives with accounts and passwords for security. Data will be stored in a locked file cabinet and on a secured-access computer. Data will not be destroyed. Only authorized individuals working directly in the study will have access to the computers.

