# Safety Assessment Risk and Injury

The primary risk in this study is the risk of falls, regardless of the prosthesis used. Fall prevention is a primary focus and the risk will be reduced by the use of harnesses, gait belts, assistive devices as needed and stand-by or contact guard assistance and supervision by researchers. All subjects will be initiated with testing and therapy sessions with simple activities, progressing on to more dynamic, complex activities when it is clear that they are safe and acclimated to the prosthesis being used. Other risks include muscle soreness from exercises during therapy sessions. To avoid this, subject will be provided with adequate rest periods and subjects will be monitored by questions regarding discomfort. Skin irritation from adjusting to a new socket fit can also be a risk. This risk will be minimized by regular check ups by a certified prosthetist, who will check for skin lesions/breakdowns.

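### Missed sessions and hospitalization can end study participation with no outcome collection afterwards, so the knee comparison may rest on selected completers; keeping scheduled assessments is a cheap improvement

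*Combined protocol and SAP*

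**What the plan says.** The Withdrawal criteria section gives three grounds: "3 or more consecutive or 5 total per leg missed sessions"; hospitalizations, with no limit on cause, length or recovery; and the principal investigator's discretion over unplanned medical events.

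Data Collection and Analysis covers the same ground more softly. After three consecutive missed visits, or an illness with or without admission, "patients may have to be withdrawn from the study". The same section uses the word session broadly, paying subjects "per session for evaluation and assessments, prosthetic fittings and training sessions", so a missed session need not be a missed training session.

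On outcomes, the design tables show monthly data collection. In each assessment period "patients will come in at regular intervals for data collection for the AMP and the 6 mwt", and the GPS window comes at the end: "During the last 2 weeks of the assessment, patients will be given GPS devices for tracking their mobility data".

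On attrition, the Study Design section says: "Due to the high rate of attrition we will randomize a total of 40 subjects". Statistical Analysis puts attrition at 30% and names a two-way repeated-measures ANOVA with prosthesis and testing session as factors. It names no analysis set and no missing-data rule. Nothing in the document separates stopping training from leaving the study, or provides for assessments after withdrawal.

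**The concern.** In a crossover the information on the knee effect comes mainly from subjects observed on both knees. A subject withdrawn in period 1 keeps whatever monthly data exist but contributes no within-subject contrast with the new foot. One withdrawn during acclimation also misses that knee's end-of-assessment GPS window, which serves Hypotheses 1 and 3. One withdrawn after the period 2 GPS window loses little.

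Exits could well be related to the knee. The safety section states: "The primary risk in this study is the risk of falls, regardless of the prosthesis used". Hypothesis 6 expects fewer falls with the C-leg, and a fall can lead to missed sessions or admission, both of which are listed grounds. The background section describes serious comorbidity, so admissions for other reasons are foreseeable too.

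A link between exit and the knee worn does not by itself bias a within-subject contrast. Bias needs one of two further conditions:

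- those who leave would have benefited more, or less, than those who stay; or
- the two sequences lose different numbers and outcomes drift between periods.

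Either is plausible here; neither is established.

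**Working it through.** **The plan's own figure.** With 40 randomised and 30% attrition, 40 × 0.7 = 28 complete and 12 leave; 28 / 0.7 = 40, so the attrition step is consistent. The 28 itself cannot be rebuilt, because no effect size or SD is given. Working backwards at two-sided 0.05 and 90% power (noncentral t), 28 pairs detect 0.64 SD of the paired difference and 34 pairs detect 0.57 SD.

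**Bias when leavers benefit differently.** Let w of 40 leave without a two-knee contrast, with a mean benefit k times that of completers. Both w and k are assumptions; the documents do not say how much attrition these criteria cause.

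- Completers only, estimate divided by all-randomised benefit: 1 / [(1 − w/40) + (w/40)k].
- Half of the leavers retained: {[(40 − w) + kw/2] / (40 − w/2)} / {[(40 − w) + kw] / 40}.

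| k | w = 4, completers | w = 4, half kept | w = 12, completers | w = 12, half kept |
|---|---|---|---|---|
| 0 | 1.11 | 1.05 | 1.43 | 1.18 |
| 0.5 | 1.05 | 1.03 | 1.18 | 1.07 |
| 1 | 1.00 | 1.00 | 1.00 | 1.00 |
| 1.5 | 0.95 | 0.98 | 0.87 | 0.95 |

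Example, w = 12 and k = 0: 1 / 0.7 = 1.43; with half kept, (28/34) / (28/40) = 40/34 = 1.18.

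**Bias from unbalanced exits.** Let π be the period 2 minus period 1 shift. The paired difference (C-leg minus mechanical) estimates the knee effect minus π in Group I (C-leg first) and plus π in Group II. With n₁ and n₂ completers in Groups I and II, a simple mean of differences is off by π(n₂ − n₁)/(n₁ + n₂). At 14 and 14 this is zero. At an assumed 16 and 12 it is −4/28, about −0.14π. The stated ANOVA factors include neither period nor sequence.

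**Precision.** Take total SD 1 and within-subject correlation ρ (assumed), fixed knee, period and sequence, and a random subject effect. Exits are split evenly by sequence and observed in period 1 only. With complete pairs only, the standard error is √[2(1 − ρ)/28]. With single-knee subjects added, it is the square root of the knee entry of (ΣXᵀV⁻¹X)⁻¹.

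| ρ | 28 pairs | 28 pairs + 12 single | 34 pairs + 6 single |
|---|---|---|---|
| 0.5 | 0.1890 | 0.1818 (−3.8%) | 0.1683 (−11.0%) |
| 0.7 | 0.1464 | 0.1431 (−2.3%) | 0.1313 (−10.3%) |
| 0.8 | 0.1195 | 0.1177 (−1.5%) | 0.1076 (−9.9%) |

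Most of the last column comes from the six extra pairs: √(28/34) = 0.907, a 9.3% cut. The gain therefore lies in keeping subjects, much more than in changing the model.

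**The case against.** The strongest defence is that this is a design choice. The protocol sets out to test efficacy, and each knee is compared after acclimation with physical therapy. Stopping subjects who miss that training is a reasonable way to study the effect in trained users, whereas keeping them shifts the question towards the effect of providing the knee. Hospitalization in this population can also change eligibility and make testing unsafe. This stands in part: it is why fully trained completers belong in a supportive analysis, and why continued assessment must depend on the investigator's judgement. It does not explain why someone who has missed sessions should also lose outcome assessments that are already scheduled.

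A reader might infer that every breach triggers removal. The documents do not support that. The procedures text is permissive, and the criteria list does not say that it is automatic. A reader might also try to predict how many subjects would reach the missed-session limits. No attendance rate is given, and the result turns on whether a session means any visit ("Subjects may be required to participate in a maximum of 45 sessions", which the protocol adds may not be needed for everyone) or only training, so no such count is offered.

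Complete-case handling is likewise an inference from how a repeated-measures ANOVA is ordinarily run; the plan neither states it nor rules it out.

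**Conclusion.** The gap is real and modest. As written, the plan allows missed sessions or an admission to end study participation and makes no provision for later outcomes, in a trial that expects 30% attrition.

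The tempting stronger reading, that knee-related exit will distort the result in favour of the C-leg, is not supported. If those who fall on the mechanical knee would have gained most from the C-leg, completers understate its benefit; if those who do badly on the C-leg leave, completers overstate it; if leavers resemble completers and exits are balanced, there is no bias. The range of 0.87 to 1.43 rests on all 12 expected exits lacking a two-knee contrast and on assumed benefits of 1.5 to 0 times that of completers. At 4 exits it narrows to 0.95 to 1.11. The share of attrition due to these criteria is unknown, and some exits, such as voluntary ones, could not be recovered by any wording.

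This is a cheap improvement to make, not a defect that invalidates the comparison.

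**What to change.** 1. Amend Withdrawal criteria and the matching text in Data Collection and Analysis so that missed sessions or a resolved hospitalization end or pause training, not study participation.
2. Where the investigator judges it safe and the subject is willing, keep the scheduled assessments for the current knee: AMP, 6MWT, end-of-period GPS, and the FES, PEQ and CPI questionnaires.
3. Let the subject go on to the second knee only with its normal fitting, acclimation and training. Offering a new knee without these would weaken the protocol's protection against falls.
4. Record the reason for each exit, the knee worn and the period, and report exits by knee.
5. Analyse all randomised subjects with any outcome data in a mixed model (fixed knee, period, sequence and session; random subject) in place of a complete-case repeated-measures ANOVA. Give the fully trained completers as a supportive analysis.

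**Cost.** Protocol and analysis wording, and assessment visits already within the 45-session maximum. Subjects who go on to the second knee use the fitting and training visits already planned for it. Some data will come from less-trained subjects, and recovery will be partial. The 10% to 11% gain requires half of the exits to reach both knees; if period 1 exits give only further data on their first knee, expect nearer 1.5% to 4%. The mixed model deals only with exits explained by data already observed.

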#### **Subject Recruitment and Screening**

Lower limb amputees will be recruited from amputee clinics at RIC and Northwestern. Clinicians at these locations will be informed that the Center for Bionic Medicine is looking for lower limb amputees who, in their judgment will fill the above criteria. Potential research subjects will be referred to [name], PT, [name], PT, [name] PT and [name], PT,. They will be provided with a contact card with contact details for the physical therapists. Potential subjects will be informed of the time commitment required and questioned regarding the inclusion/exclusion criteria.

In addition, research staff on the study will identify potential subjects from RIC's Cerner Information Systems. Once a dysvascular transfemoral amputee has been identified, study staff will contact the subject's clinician and get permission to pre-screen as a potential subject. If clinician agrees, clinician may contact potential subject or study staff will contact the potential subject on behalf of clinician, initially with a letter followed by a phone call to the potential subject.

A recruitment flyer will be distributed to prosthetists' offices (e.g. at Hanger, Scheck and Siress) for posting/handing out to potential clients who may be interested in learning more or participating in the study.

Study staff will also post information about the study by e-mailing members of the Midwest Chapter of the American Academy of Orthotists and Prosthestists, which is available only to prosthetic and orthotic professionals who are members and live within the boundaries of Wisconsin, Illinois and Indiana. Information about this organization may be found at: http://www.oandp.org/membership/chapters/midwest/. The same message will also be posted on OANDP-L ([contact]) which is the listserver for the exchange of information for orthotics and prosthetics professionals..

Finally, [name] will screen the potential subjects to ensure that they meet the inclusion/exclusion criteria.

# **Efficacy Assessment**

Microprocessor knees have shown to be very effective to improve community mobility and quality of life in the K3&K4 amputee population. This protocol seeks to test the efficacy of the microprocessor knee (C-leg) in the K2 dysvascular population.

# Safety Assessment Risk and Injury

The primary risk in this study is the risk of falls, regardless of the prosthesis used. Fall prevention is a primary focus and the risk will be reduced by the use of harnesses, gait belts, assistive devices as needed and stand-by or contact guard assistance and supervision by researchers. All subjects will be initiated with testing and therapy sessions with simple activities, progressing on to more dynamic, complex activities when it is clear that they are safe and acclimated to the prosthesis being used. Other risks include muscle soreness from exercises during therapy sessions. To avoid this, subject will be provided with adequate rest periods and subjects will be monitored by questions regarding discomfort. Skin irritation from adjusting to a new socket fit can also be a risk. This risk will be minimized by regular check ups by a certified prosthetist, who will check for skin lesions/breakdowns.

#### Benefits

The benefits from this study to the individual subjects will only be related to similar physical therapy sessions they would receive as part of their rehabilitation. Although the immediate benefits of the study to the individual are limited, the entire community of transfemoral amputees stands to benefit with a better understanding of functional gains and quality of life changes with different prosthetic components. Upon completion of the

study, the participant may choose to keep the prosthetic foot used in the study if continued use is approved by their clinical prosthetist.

